Methods: The proposed study will be a double-blind, placebo-controlled, randomized cross-over challenge study, in which people with schizophrenia are pretreated with either high-dose NAC, 140 mg/kg up to a maximum of 15 g, or placebo, then receive TRYP, 6 gms. We will collect baseline and post-treatment KYNA and kynurenine; clinical; neuroimaging; and cognitive measures. Participants (n=100) will be of either sex and any race, between 18 - 55 years old, with a Diagnostic and Statistical Manual of Mental Disorders (DSM)-5 (20) diagnosis of schizophrenia or schizophreniform or schizoaffective disorder. A best estimate diagnostic approach will be utilized in which information from the Structured Clinical Interview for DSM-5 (SCID; 21) is supplemented by information from family informants and medical records to generate a diagnosis. Participants will be judged by their clinician to be clinically stable. We will not restrict the type of antipsychotic with which the participant is treated or the use of concomitant medications; there is little evidence of a differential effect of first and second generation antipsychotics on KYNA levels (22). The inclusion and exclusion criteria are:

Inclusion Criteria:

- 1) Males and females
- 2) Age: 18 to 55 years
- 3) DSM-5 Criteria for schizophrenia, schizoaffective disorder or schizophreniform disorder (documented by SCID)
- 4) Prescription of antipsychotic medication for at least 60 days and constant dose for 7 days prior to study entry (either first or second generation antipsychotics permitted)
- 5) Female participants must agree to use a medically accepted means of contraception

Exclusion Criteria:

- 1) DSM-5 alcohol or substance use disorder in the last 3 months, other than nicotine and cannabis (documented by SCID). Only participants meeting a moderate to severe cannabis use disorder will be excluded.
- 2) History of an organic brain disorder; intellectual disability; or a medical condition, whose pathology or treatment could alter cognition or increase their safety risk of protocol participation
- 3) Active disorders that have been reported to affect tryptophan metabolism or interfere with absorption will be excluded (Acute Intermittent Porphyria, Celiac Disease, Crohn's Disease, Irritable Bowel Syndrome).
- 4) Excessive self-reported daily caffeine intake, defined as intake exceeding 1000mg or the equivalent of 10 cups of coffee
- 5) Pregnancy or lactation secondary to pregnancy

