- 6) Presence of MRI contraindications (e.g. pacemakers)
- 7) Regularly scheduled use of monoamine oxidase inhibitors, migraine headache medications (triptans) and dextromethorphan. Excludes only daily use, prn permitted.

Participant Recruitment: Potential participants with SRDs will be recruited from three sources: the Maryland Psychiatric Research Center (MPRC) clinical programs: the Outpatient Research Program (ORP), the Treatment Research Program (TRP), and the First Episode Clinic (FEC); local outpatient mental health centers; and a standing recruitment database, from which we have enrolled participants in previous MPRC clinical trials. Potential MPRC and community participants will be identified primarily through chart review or nomination by their primary clinicians who are aware of study entry criteria and demands, and have been asked to identify clinically stable patients who may be interested in research participation. MPRC and community participants may also be self- or peer-referred for this study. Participants may also be recruited from internet based advertising (HP-00061828) that will refer interested participants to the MPRC web site

Study Assessments:

Clinical Assessments: The following rating scales will be used to characterize the baseline clinical state of the study sample and to assess whether there any changes in the clinical state of the study participants during their participation in each of the Challenge Phase visits: the Brief Psychiatric Rating Scale (BPRS; 23) total score will be used to measure global psychopathology. The four BPRS positive symptom items - conceptual disorganization, suspiciousness, hallucinatory behavior, and unusual thought content - will be used to measure positive psychotic symptoms. The Scale for the Assessment of Negative Symptoms (SANS; 24) total score will be used to measure negative symptoms; Calgary Depression Scale (CDS; 25) total score will be used to measure depressive symptoms; and Clinical Global Impression Scale (CGI; 26) severity of illness item will be used to confirm clinical stability prior to entry into the Challenge Phase and assess global changes during the Challenge Phase.

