
Two hours after ingestion of NAC/placebo, participants will undergo the post-treatment imaging studies. We chose to begin scanning 120 minutes after NAC and 90 minutes after TRYp, because 1) our preclinical data show that NAC administered 30 minutes prior to TRYp administration attenuates KYNA production through KAT II inhibition; 2) our preliminary data suggests that peripheral kynureine and KYNA levels are initially elevated 30 minutes after TRYp ingestion, and continue to increase over the next three hours and remain elevated for at least 3.5 hours; 3) NAC pharmacokinetic studies have demonstrated that peak serum levels occur within 90-150 minutes of administration and remain elevated for 4-6 hours (46,48); and 4) GSH, an indirect measure of NAC in the CNS, starts to elevate 50 minutes after NAC administration, reaches maximal elevation 90-110 minutes after oral NAC administration and remains elevated for at least 120 minutes (49). Thus, there should be sufficient time to complete the post-treatment MRI, clinical, laboratory, and cognitive assessments. A non-blind pharmacist will dispense all study medications. The blind will be broken

only if a medical emergency requires this information. If this occurs, the participant will be withdrawn from the study. The day after each challenge day, the RA will follow-up with the participant, via telephone, to evaluate whether there are any persistent effects from the receipt of the challenge medications. Any concerns of the participant will be reported immediately to the study physician.

Procedures/Assessments	Evaluation Phase (2 weeks)	Challenge Visit #1:	Challenge visit #2:	Initials
Informed Consent, Evaluation to Sign Consent	X			
Medical Screening: Medical History, physical exam, blood draw, urinalysis, toxicology screen, pregnancy test (females), EKG, medication use screening, caffeine use screening, Birth Control Selection (females)	X			
MRI screening	X			
Clinical Stability Determination (for participants with schizophrenia or a related disorder only): 2 unchanged CGIs	X			
Scheduling of challenge day visits	X			
Participant arrival at Brief Stay Unit (BSU) Review of Study Procedures		7:15 am	7:15 am	
Urine pregnancy (females); expired CO**; urine toxicology and breath alcohol testing		7:30 am	7:30 am	
Insertion of heparin lock		7:40 am	7:40 am	
Vital signs, SEC, SSS;		7:50 am	7:50 am	

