Our project is uniquely based on an emerging body of evidence, which suggests that disturbances in the kynureine pathway, especially those that lead to increased levels of KYNA, may be of critical importance in the pathophysiology of cognitive impairments in schizophrenia. Second, the proposed study is the first experimental test of brain and behavioral effects of KAT II inhibition in human subjects. The results from the study would provide unique insights into the mechanisms underlying the role of KYNA in the pathophysiology of schizophrenia. Third, although the use of NAC is not innovative, the hypotheses that: i) NAC may work through its ability to inhibit KAT II; ii) there may be large effects in a subgroup of people with schizophrenia, i.e., those characterized by high serum KYNA levels or low KMO activity; and iii) the use of high NAC doses (>5 times other clinical studies) are innovative. Fourth, in order to provide a comprehensive evaluation of the effects of NAC on various KYNA related manifestations of the illness, we will use a multi-dimensional evaluation of the effects of NAC on KYNA production in schizophrenia, which will include behavioral, biochemical, neuroimaging, and phenomenological assessments. Fifth, the parallel assessments across the two preclinical studies and two clinical studies will provide a framework to bi-directionally inform the interpretation of the results of these studies. The ability to translate the results across each of the proposed studies is critically important for the proposed Center. Finally, the demonstration that NAC blocks the impact of increased KYNA levels in people with schizophrenia will importantly support the development of KAT II inhibitors for the enhancement of cognition in schizophrenia.

References:

2. Miller, C. L., Llenos, I. C., Dulay, J. R., and Weis, S. (2006) Upregulation of the initiating step of the kynurene pathway in postmortem anterior cingulate cortex from individuals with schizophrenia and bipolar disorder. *Brain Res.* 1073-1074, 25-37. PMID: 16448631

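### Nothing in the eligibility rules, washout or pre-visit instructions addresses existing use of N-acetylcysteine or tryptophan products, so a regular user of a study agent can enter and the placebo day may not be NAC-free for that person

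*Combined protocol and SAP*

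**What the plan says.** The general rule in Methods is "We will not restrict the type of antipsychotic with which the participant is treated or the use of concomitant medications". The reason given concerns only antipsychotics and KYNA; other medicines are not discussed.

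The Exclusion Criteria then limit medicines and conditions in three ways:

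- Exclusion 7: "Regularly scheduled use of monoamine oxidase inhibitors, migraine headache medications (triptans) and dextromethorphan", with the qualifier "Excludes only daily use, prn permitted".
- Exclusion 3: "Active disorders that have been reported to affect tryptophan metabolism or interfere with absorption will be excluded". This covers disorders, not products.
- Exclusion 2 covers, among other things, "a medical condition, whose pathology or treatment could alter cognition or increase their safety risk of protocol participation". This could catch some people through the treatment of an illness, but it names neither NAC nor tryptophan.

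The procedures table lists "medication use screening, caffeine use screening" in the Evaluation Phase, with no rule on which medicines make a candidate ineligible. The fasting instruction under Challenge Phase deals with food and drinks and does not mention medicines or supplements. The covariates named under Specific Aims #1 and #2 are age and sex, plus unspecified others.

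**The concern.** The trial compares a day with NAC against a day without it, both under a tryptophan challenge. The plan controls several lesser influences on the measurements: caffeine intake, fasting, nicotine timing and protein-free snacks. It does not control outside use of the two agents under test.

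A regular NAC user could reach the placebo visit with NAC on board. If background NAC inhibits KAT II at all, it would blunt the KYNA rise after tryptophan on the comparator day, and the NAC-placebo difference would shrink. Randomising the order does not cancel this, because the contrast shrinks in both sequences. Pre-dose glutathione, which the plan treats as an indirect marker of NAC in the brain, could also start raised. That matters for the hypothesis that the imaging effects are independent of glutathione change.

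For a tryptophan user the issue is narrower. The 6 g challenge is given on both days, so a stable background intake mainly moves the starting kynurenine and KYNA. Baseline KYNA is a moderator in Exploratory Aim 2.

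**Working it through.** **1. Is a regular user eligible?** Taking the criteria in turn, exclusion 7 does not list NAC or tryptophan. Exclusion 3 needs an active disorder. Exclusion 2 needs a medical condition, so a person taking a product simply as a supplement is not caught. The medication screen has no rule attached. Read as written, such a person is eligible.

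**2. Can background NAC overlap the placebo challenge?** Challenge Phase puts the serum peak at 90-150 minutes and elevation at 4-6 hours. I assume that this is counted from ingestion and applies to the background product. The table sets arrival at 7:15, study drug at 10:35, tryptophan at 11:05 and the second scan at 12:20.

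- Dose taken before midnight: elevated until 6:00 at the latest (0:00 + 6 h), before arrival. No serum overlap.
- Dose taken at 7:00 (assumed): elevated until 11:00 (7:00 + 4 h) to 13:00 (7:00 + 6 h). This covers placebo dosing and, over most of that range, the tryptophan dose. Towards the upper end it reaches the start of the second scan.

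Overlap is therefore possible but depends on timing. Longer-lasting effects of regular use cannot be sized from the documents.

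**3. Reproduce the plan's power.** Inputs from Specific Aims #1 and #2: 60 completers, d = 0.37, alpha 0.05. I assume a two-sided test and a paired analysis. The noncentrality is d × √n = 0.37 × √60 = 2.866 with 59 degrees of freedom and critical t = 2.001. Power is 0.805, matching the stated 80%.

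**4. Dilute the contrast.** Let f be the share of participants who use NAC and r the share of the contrast that each loses. Then d_eff = 0.37 × (1 − f × r), with the standard deviation held constant. Both f and r are assumptions.

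| f | r | d_eff | Power, 60 completers |
|---|---|---|---|
| 0 | – | 0.370 | 0.805 |
| 2% | 0.5 | 0.366 | 0.797 |
| 5% | 0.5 | 0.361 | 0.785 |
| 10% | 0.5 | 0.352 | 0.764 |
| 2% | 1 | 0.363 | 0.789 |
| 5% | 1 | 0.352 | 0.764 |
| 10% | 1 | 0.333 | 0.718 |

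**5. Sensitivity to the number of completers.** The plan pairs 20% attrition of 100 with 60 completers, but 100 × 0.8 = 80. With 80 completers, power is 0.905 without dilution and 0.837 at f = 10%, r = 1.

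**The case against.** The strongest reply is that affected people would lose only part of the contrast and may be few.

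- **Dose.** The plan says "the use of high NAC doses (>5 times other clinical studies) are innovative" and chose its dose because its preclinical work found KAT II inhibition at high doses. On that rationale, background NAC at an ordinary dose would produce little of the tested effect, and the user still receives the full study dose on the NAC day. This stands, and it makes r = 1 an outer bound.
- **Change scores.** The analysis compares change from baseline within person. With baseline measured before dosing on each day, a stable background level is partly absorbed. This also stands in part, but it does not restore an untreated response to tryptophan on the placebo day.
- **Existing checks.** Consenting describes chart review and a primary clinician's judgement of suitability, and a medication screen is scheduled. These may bring use to light, but none says what to do about it.
- **Prevalence.** No figure is given. One recruitment source is "a standing recruitment database, from which we have enrolled participants in previous MPRC clinical trials". A reader might infer that people from other NAC studies, even concurrent ones, will enter. The text does not say that those trials involved NAC or overlap with this one.

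A reader might also infer that the placebo day is contaminated for every NAC user, or that each user contributes no contrast. The 4-6 hour figure does not support the first, and the dose rationale makes the second unlikely.

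**Conclusion.** The gap holds: under the written rules a regular user of NAC or tryptophan products is eligible, and neither the visit instructions nor the analysis deals with that use. For NAC users the placebo comparator may be partly compromised, depending on dose and timing. For tryptophan users the consequence is mainly a shifted baseline, including an exploratory moderator.

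The size rests on an assumed prevalence. At 2% to 10% NAC users, the loss of power is between 0.008 (0.805 − 0.797) and 0.041 (0.805 − 0.764) with half the contrast lost. It is between 0.016 (0.805 − 0.789) and 0.087 (0.805 − 0.718) with all of it lost. A reader might conclude that the trial is underpowered for this reason. The documents do not support that, because the lowest figure needs both a 10% prevalence that no source supplies and total loss of contrast. The case for acting is that the remedy is cheap and that use not recorded prospectively may be hard to recover later.

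**What to change.** - Reconcile the Methods sentence on concomitant medications with exclusion 7, for example by adding 'except as listed'.
- Add an eligibility criterion on current use of NAC or tryptophan products, prescribed or over the counter. The sponsor should set the abstention window and make it cover both challenge visits.
- Ask about supplements explicitly in the medication screen already scheduled. Record any use, so that a sensitivity analysis can be run without the affected participants.

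The cost is one criterion and one question in an existing form. The downside is that a few candidates will be excluded or deferred.

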Challenge Phase (Visits 3 and 4): The Challenge Phase will utilize a double-blind, placebo-controlled, randomized cross-over design. A permuted block randomization system (block sizes 2 or 4) will be used to randomly assign participants to NAC, 140 mg/kg up to a maximum of 15 g, or placebo. There will be two Challenge Phase visits, which will be at least two weeks apart. On the day of each visit, participants will arrive at the MPRC Brief Stay Unit (BSU) at 7:15AM; all participants will have fasted since midnight. Participants are asked to avoid eating food of any kind after midnight the evening prior to visits 2 and 3. Participants are encouraged to drink water but to strictly avoid food, coffee, alcohol, and sodas. Participants who regularly use nicotine products will be given short breaks to use their products in order to avoid effects of nicotine withdrawal. The nicotine breaks will occur at least 60 minutes prior to the neuroimaging sessions in order to minimize the effect of nicotine on any of the neuroimaging measures. A heparin lock will be inserted for the repeated laboratory assessments and the initial clinical, cognitive, laboratory, and safety assessments will be conducted (including urine pregnancy test for female participants). Participants will then undergo their pre-treatment imaging studies. Upon completion of the imaging studies, participants will receive NAC, 140 mg/kg up to a maximum of 15 g, or placebo. They will receive the other study medication on the second visit (i.e., placebo or NAC). The proposed NAC dose has been used extensively to treat acetaminophen poisoning. We selected this high dose based on our preclinical studies showing high doses inhibit KAT II. There is extensive safety data available with this dose. We selected the effervescent formulation to minimize gastrointestinal and other side effects. In addition, the effervescent formulation is flavored, which helps to increase the tolerability and to mask the smell typically associated with NAC (46). Thirty minutes after NAC/placebo administration participants will receive TRYp, 6 grams in oral slurry form. The dose was chosen based on previous work showing cognitive effects to be associated with doses above 5 grams (47) and our the preliminary data from our previous Conte Center project, in which we demonstrated that TRYp (6 grams) produces a robust increase in KYNA and kynureine and reduction in the ASL measure of CBF in participants with schizophrenia and related disorders.

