Laboratory Assessments (1): kynureine pathway metabolites, inflammatory markers, oxidative stress and other related markers				
Nicotine Break (1)*		7:55 am	7:55 am	
Protein Free Snack				
Cognitive Measures (1): MCCB measures: HVLT-R, BACS Symbol Coding, BVMT, CPT-IP, WMS®-III, LNS;		8:00 am	8:00 am	
Clinical Assessments (1): BPRS, SANS, CDS, CGI		8:45 am	8:45 am	
Neuroimaging Studies (1)		9:15 am	9:15 am	
Nicotine Break (2)		10:30 am	10:30 am	
Oral Administration of N-acetylcysteine (NAC) 140 mg/kg up to a maximum of 15gm or placebo		10:35 am	10:35 am	
Oral Administration of Tryptophan 6 grams		11:05 am	11:05 am	
Lunch		11:25 pm	11:25 pm	
Vital signs, SEC, SSS		12:05 pm	12:05 pm	
Laboratory Assessments (2)				
Neuroimaging Studies (2)		12:20 pm	12:20 pm	
Laboratory Assessments (3)		1:35pm	1:35pm	
Protein Free Snack		1:40 pm	1:40 pm	
Nicotine break (3)				
Cognitive Measures (2)		1:55 pm	1:55 pm	

Clinical Assessments (2)		2:40 pm	2:40 pm	
Vitals, SEC, SSS		3:05 pm	3:05 pm	
Laboratory Assessments (4)				
Participant discharged. If participant has not returned to pre-challenge baseline, they will be reassessed every 30 minutes until ready		3:15 pm	3:15 pm	

*Nicotine breaks are optional and subject to occur at different times as long as they do not occur within 60 minutes prior to the neuroimaging studies.

**Due to the COVID-19 pandemic, the expired CO breathalyzer assessment is an optional procedure.

Randomization and Blinding: This will be a double-blind, placebo-controlled, randomized cross-over challenge study. Participant randomization will use a permuted block randomization system (block sizes 2 or 4), in which treatment assignment order is random within each block, with an equal number of participants assigned to each treatment, to generate a list of treatment assignments. Thus, it will be difficult to ascertain the next treatment assignment, even if a participant becomes unblinded, while any imbalance in the number of participants between the treatment groups will be kept within tight limits. All raters, investigators and other staff will be blind to treatment assignment except for the research pharmacist. The research pharmacist does not participate in assessing any of the primary symptom or side effect dependent variables and conveys no information about treatment assignment to participants or staff except in a medical emergency.

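### Exclusion 7 limits MAOIs, triptans and dextromethorphan by frequency of use only, and no scheduled step asks about recent intake before tryptophan on either challenge day

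*Combined protocol and SAP*

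**What the plan says.** Exclusion 7 in the Methods section of the combined protocol and SAP covers three drug classes: "Regularly scheduled use of monoamine oxidase inhibitors, migraine headache medications (triptans) and dextromethorphan. Excludes only daily use, prn permitted". No washout or last-dose interval follows. The paragraph before the criteria sets the general policy: "We will not restrict the type of antipsychotic with which the participant is treated or the use of concomitant medications".

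In the Procedures/Assessments table, the Medical Screening row includes "EKG, medication use screening, caffeine use screening, Birth Control Selection (females" and is marked for the Evaluation Phase only. On each challenge day the 7:30 am row reads "Urine pregnancy (females); expired CO; urine toxicology and breath alcohol testing" (the CO test is footnoted as optional). The 7:50 am row adds vital signs, the Side Effect Checklist (SEC), the sleepiness scale and the first blood draw. NAC or placebo follows at 10:35 am, and the 11:05 am row is "Oral Administration of Tryptophan 6 grams".

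The Challenge Phase text tells participants what to avoid beforehand: "Participants are encouraged to drink water but to strictly avoid food, coffee, alcohol, and sodas". It does not mention medicines.

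**The concern.** Tryptophan is given as one acute dose on each of two days. If a drug class matters enough for daily users to be excluded, the natural question on those days is whether the drug is on board at dosing. A rule about frequency of use does not answer it: an occasional user who took a dose that morning is eligible and may have the same drug on board as an excluded daily user.

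What is at stake is participant safety and staff's ability to act before dosing. With no question scheduled, recent intake might come to light only if the participant volunteers it or after tryptophan has been given. The protocol rechecks other changeable conditions on the day: pregnancy, toxicology and breath alcohol. It also sets a time limit for nicotine, at least 60 minutes before imaging. The drugs in exclusion 7 get neither a recheck nor a time limit.

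**Working it through.** The plan states no figure on this point. The check is a reading of the schedule, plus clock differences.

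**1. Is there a timing limit?** Exclusion 7 gives none, and the concomitant-medication sentence in Methods adds no restriction.

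**2. Where is medication use asked about?** Scheduled medication screens: Evaluation Phase 1, challenge visits 0 of 2. The Challenge Phase text puts the two challenge visits at least two weeks apart, so by the second one the only scheduled screen is at least two weeks old.

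**3. Could another pre-dose step serve?** The challenge-day steps before 11:05 am, from the table, are:

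| Time | Step | Asks about medicines taken? |
|---|---|---|
| 7:15 | Arrival, review of procedures | Content not described |
| 7:30 | Pregnancy, CO, toxicology, breath alcohol | No; the toxicology panel is not described as covering these drugs |
| 7:40 | Heparin lock | No |
| 7:50 | Vital signs, SEC, sleepiness scale, blood draw | No; the SEC records side effects, not intake |
| 7:55 | Optional nicotine break, snack | No |
| 8:00 | Cognitive tests | No |
| 8:45 | Clinical ratings | No |
| 9:15 | Imaging | No |
| 10:30 | Optional nicotine break | No |
| 10:35 | NAC or placebo | No |

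**4. What does the timetable allow?** Differences between scheduled times:

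- Arrival to NAC/placebo: 10:35 − 7:15 = 200 min (3 h 20 min).
- Arrival to tryptophan: 11:05 − 7:15 = 230 min (3 h 50 min).
- 7:30 block to cognitive testing: 8:00 − 7:30 = 30 min.
- 7:30 block to NAC/placebo: 10:35 − 7:30 = 185 min (3 h 05 min).
- 7:30 block to tryptophan: 11:05 − 7:30 = 215 min (3 h 35 min).
- Tryptophan to the first timed vital-signs and SEC check: 12:05 pm − 11:05 am = 60 min.
- Tryptophan to the last timed check: 3:05 pm − 11:05 am = 240 min (4 h).

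A drug taken before arrival therefore precedes tryptophan by at least 3 h 50 min. The documents do not show whether that is long enough for any of the three classes. A question at 7:30 am would leave time to stop before any testing or study drug. These differences show that the fix is feasible; they do not measure harm.

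**The case against.** The strongest reply is that prn use was allowed on purpose and that the documents state no hazard. Exclusion 7 separates daily from occasional use in plain words, and Risks Related to Tryptophan mentions no drug interaction. All that can be read from the text is that daily use concerned the authors. That stands. A reader might infer that a prn dose near tryptophan is known to be dangerous, or that prn users should be excluded. The documents support neither inference.

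Second, there are other safeguards. Exclusion 2 lets the investigator turn away someone whose treatment raises the safety risk. The Consenting section requires the primary clinician's approval and a chart review. The plan provides for IRB and DSMB review. After dosing there are vital signs and SEC checks, a staff evaluation before discharge, reassessment every 30 minutes if the participant has not returned to baseline, and a next-day call. These narrow the gap. But the entry safeguards set no challenge-day timing, and the monitoring can detect a problem only after tryptophan has been given.

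Third, a reader might infer that nobody asks. That goes too far. The removed consent pages may carry an instruction, the content of the 7:15 am procedure review is not described, and staff may ask as routine. The supportable statement is that the available protocol text schedules no such question.

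Fourth, a hold rule is in effect a timing limit on prn use. That is correct and should be said openly. Eligibility does not change, but the allowance becomes conditional on challenge days.

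**Conclusion.** The point holds as a modest improvement to consider. Exclusion 7 regulates three drug classes by frequency alone, and none of the scheduled steps on either challenge day is described as establishing recent intake before tryptophan. The conclusion rests on the available protocol text and on one inference: because daily use is excluded, the sponsor has some concern about these drugs that may also apply to a recent single dose. The documents do not confirm that inference, since they give no reason for the exclusion.

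Clinical risk and the number of participants affected cannot be calculated, because neither the size of any interaction nor the rate of prn use is given. A reader might also infer a biased treatment comparison. Nothing in the documents shows that recent use would differ between NAC and placebo days, so no such claim is made.

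**What to change.** Keep prn users eligible, and make two additions for both challenge visits:

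1. In the 7:30 am block, ask about recent medicines: drug, dose and time last taken, including prn and over-the-counter products.
2. Have the sponsor set a minimum interval since the last dose for each of the three classes. If a listed drug was taken within its interval, the study physician holds and reschedules before the 8:00 am testing, keeping the two-week minimum between challenge visits.

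State in the protocol that this places a challenge-day timing limit on the prn allowance. Name the visits as Visits 3 and 4, as the Challenge Phase heading does. The fasting sentence says "Participants are asked to avoid eating food of any kind after midnight the evening prior to visits 2 and 3"; that numbering slip is a separate matter, but copying it would miss Visit 4.

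The written change is one schedule line, three intervals and a short hold rule, with a brief question at each visit. The real cost is some rescheduled challenge days and some added dropout risk in a two-visit crossover. Both depend on the prn rate and on the intervals chosen, so neither can be quantified from the documents.
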